2.3 Study subjects

2.3.1 Subject disposition

The number of subjects in each study population (i.e. FAS, PP, and Safety) will be summarized by site and in total.

The disposition of subjects (including reasons for screening failures and withdrawals) will be presented by treatment group and in total. Subject accountability will be presented by treatment and visit.

2.3.2 Withdrawals and Protocol deviations

All withdrawn subjects will be listed individually, including at least subject number, date and reason for withdrawal, and last visit performed. Subjects with CSP deviations will be listed individually, including subject number and observed deviation. Depending on the seriousness of the deviation, Group B subjects might be excluded from the PP population, which shall be documented prior to database lock.

For this study, the protocol deviations that will exclude Group B subjects from PP are identified (but not limited to) in Table 3 below.

Table 3. Protocol deviations

Deviation	
GENERAL	
	Visit out-of-window
*	Follow-up at Month 12 after baseline performed earlier than 2 weeks before or later than 4 weeks after the scheduled visit for the treatment and control group
EFFECTIVENESS	
	Primary effectiveness endpoint
*	No baseline MMVS by blinded evaluator available
*	MMVS by blinded evaluator missing at Month 12 after baseline
	Treatment
*	Treatment not performed according to randomization
OTHER	
	Inclusion/exclusion criteria
*	Violate any inclusion or exclusion criteria considered to have substantial effect on the primary effectiveness endpoint
	Concomitant medication/procedures
*	Take any prohibited concomitant medication/procedures considered to have substantial effect on the primary effectiveness endpoint

Deviations from the SAP will be documented in the CSR.

 GALDERMA	Title 43CHSA1803 Statistical Analysis Plan - Sculptra China	Doc id MA-40407
--	---	---------------------------

2.3.3 Demographic characteristics

Subject demographic and baseline characteristics data will be summarized for the FAS population by treatment group and in total.

2.3.4 Medical and surgical history, concomitant medication/procedures

All summaries will be done by treatment group based on the FAS population. Concomitant medications will be coded using the World Health Organization (WHO) Drug Dictionary. Medical History will be coded according to MedDRA.

The number and percent of subjects reporting medical history, and the number of events will be summarized by system organ class (SOC), in total and for ongoing events.

The number and percentage of subjects reporting concomitant medications will be summarized by treatment. In addition, the number and percent of subjects reporting concomitant medication, and the number of drugs (total number and the number of ongoing drugs), will be summarized by reason. The same summary will be done for concomitant procedures/treatments. Also, the number and percent of subjects, and the number of drugs, will be summarized by ATC code. Concomitant medications that started due to an AE will be summarized separately.

2.4 Effectiveness analysis

2.4.1 Datasets analyzed

All effectiveness variables will be analyzed using the FAS population. The primary analysis will be repeated using the PP population. If it is deemed necessary, other analyses will be repeated using the PP population.

2.4.2 Handling of missing data

Different assumptions regarding the missing data will be used. For the primary effectiveness analysis, missing values in the FAS will be assumed to be missing due to lack of effect. Therefore missing data up to the Month 12 visit will be imputed using the baseline observation carried forward (BOCF) method. As an alternative approach, missing data will be assumed to be unrelated to treatment effect. To impute data under this assumption, missing data up to the Month 12 visit will be imputed using the hot deck method. Both of these alternatives will estimate the effectiveness of the treatment policy (irrespective of use of not allowed treatments, procedures, or medications) rather than the true, clinical treatment effect.

To obtain an estimate of the true, clinical treatment effect, the primary effectiveness analysis will be performed using the PP population.

All other endpoints will be analysed on available data (observed cases - OC), i.e. no imputations will be done.

Use of Hot Deck

Each missing value in MMVS at Month 12 visit (recipient) will be imputed with a non-missing (observed) value from a subject randomly selected from the same imputation class (donor). Imputation classes will be defined based on treatment group (Sculptra or Control group), baseline MMVS value (2, 3 or 4 as assessed by the blinded evaluator) and age group (<55 vs. ≥ 55). Alternative imputation classes may be used if deemed necessary.

	Title 43CHSA1803 Statistical Analysis Plan - Sculptra China	Doc id MA-40407
--	---	---------------------------

Effective date: 2019-10-24 08:59

Effective

Version: 1.0

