If a subject has used any of the above prohibited medications or performed any of the above prohibited procedures, a protocol deviation will be documented. The subject should continue in the study for the scheduled follow-up visits.

 GALDERMA	Title 43CHSA1803 Clinical Study Protocol	Doc id MA-39381
---	--	---------------------------

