#### *4.8.1.6 24M ( $\pm 4w$ ) Final visit or Early termination*

- Weight
- Photography
- MMVS (by Blinded Evaluator and treating investigator)
- GAIS (by treating investigator and subject)
- Subject satisfaction questionnaire
- Pregnancy test for childbearing potential women
- Concomitant medications/procedures
- AE since last visit
- Laboratory tests (Only performed at early termination if termination occurs before 12 months visit)
- Study termination

*Effective*

Version: 2.0

 GALDERMA	Title 43CHSA1803 Clinical Study Protocol	Doc id MA-39381
--	--	---------------------------

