1.4.2 Secondary effectiveness endpoints

- Percentage of responders, defined by at least 1 point improvement from baseline on the MMVS on both sides of the face concurrently, as measured by the blinded evaluator at 6, 9, 18 and 24 months in Treatment Group, and at 6 and 9 months in Control Group.
- Percentage of responders, defined by at least 1 point improvement from baseline on the MMVS on both sides of the face concurrently, as measured by the treating investigator at 6, 9, 12, 18 and 24 months in Treatment Group, and at 6, 9 and 12 months in Control Group.
- Volume change from baseline over time of the right and left midface areas combined, as measured by digital 3D photography at 6, 9, 12, 18 and 24 months in Treatment Group, and at 6, 9 and 12 months in Control Group.
- Percentage of responders, defined by having “Improved”, “Much improved” or “Very much improved” according to the Global Aesthetic Improvement Scale (GAIS) on both sides of the face combined, as assessed by the subject and the treating investigator at 6, 9, 12, 18 and 24 months in Treatment Group, and at 6, 9 and 12 months in Control Group.
- Percentage of subjects in each response category of each question in the subject satisfaction questionnaire in Treatment Group at 6, 9, 12, 18 and 24 months.

Note: Time of the Follow up visits at 6, 9, 12, 18 and 24 months is calculated from baseline/randomization.

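### Month 18 and 24 response rates can overstate persistence: leavers go uncounted, ratings after another volume-adding midface procedure stay in, and nothing bounds either effect

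*SAP*

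**What the plan says.** SAP 1.4.2 lists MMVS response "as measured by the blinded evaluator at 6, 9, 18 and 24 months in Treatment Group" among the secondary endpoints. Treating-investigator MMVS, GAIS and 3D volume are also listed at Months 18 and 24. The Control Group has no visit after Month 12, so these are single-arm results.

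For the primary analysis, SAP 2.4.2 makes two assumptions. Under BOCF, "missing values in the FAS will be assumed to be missing due to lack of effect". Under the hot-deck alternative, "missing data will be assumed to be unrelated to treatment effect". Both apply only up to Month 12. For everything else: "All other endpoints will be analysed on available data (observed cases - OC), i.e. no imputations will be done". SAP 2.4.1 puts all effectiveness variables on the FAS. The titles of Tables 3-20, 3-22, 3-25 and 3-27 carry the FAS and OC labels.

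Protocol 4.6 prohibits, among other things, fillers, lifting threads, permanent implants and fat injection below the lower orbital rim. Where one is used, a deviation is recorded and "The subject should continue in the study for the scheduled follow-up visits". The PP set can exclude for this, but the criterion in SAP Table 3 is: "Take any prohibited concomitant medication/procedures considered to have substantial effect on the primary effectiveness endpoint". Repeating secondary analyses on PP is optional (SAP 2.4.1).

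**The concern.** Two features act on the Month 18 and 24 figures.

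- **Leavers.** A subject not seen at the visit is in neither numerator nor denominator. The plan takes lack of effect seriously enough as a reason for missing data to build its primary analysis on it. It has no counterpart for the second year, although Protocol 6.7.4 allows that a result may not persist.
- **Other procedures.** No SAP rule excludes, censors or recodes a rating made after a prohibited volume-adding procedure. Continued follow-up, the FAS and observed cases together keep that rating in as a Sculptra result. PP does not help for a procedure after the Month 12 visit, because it cannot affect a rating already made.

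At stake is how well the late responder rates and volumes describe persistence in a study meant for registration. There is no concurrent control at these visits, so any bias passes straight into the reported figure.

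**Working it through.** **Inputs.** The plan's 126 reproduces from SAP 2.7: 100/0.8 = 125 and 50/0.8 = 62.5, rounded up to 63; at 2:1, 2 × 63 = 126. I assume all 126 are treated and so enter the FAS. The plan gives no Month 18 or 24 response rate, no loss rate after Month 12 and no rate of other procedures. I borrow 60% response and 20% loss from the Month 12 sample-size calculation. The procedure counts (5 or 10 of those seen) are assumptions with no source in the documents.

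**Step 1: observed cases against all subjects.** Observed-case rate = responders/seen. Missing-as-non-responder rate = responders/126. Best case = (responders + missing)/126. Counts are rounded to whole subjects.

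| Missing | Seen | Responders | Observed cases | Missing = non-responder | Missing = responder |
|---|---|---|---|---|---|
| 13 (10%) | 113 | 68 | 60.2% | 54.0% | 64.3% |
| 25 (20%) | 101 | 61 | 60.4% | 48.4% | 68.3% |
| 38 (30%) | 88 | 53 | 60.2% | 42.1% | 72.2% |

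At 20% missing, the exact 95% intervals are 50.2 to 70.0% (61/101) and 39.4 to 57.5% (61/126).

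**Step 2: direction of the observed-case effect.** Bias = share missing × (stayers' rate − leavers' rate). With 20% missing and stayers at 60%:

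- leavers at 0% (the BOCF assumption): 0.20 × 0.60 = +12 points
- leavers at 30%: 0.20 × 0.30 = +6 points
- leavers at 60% (the hot-deck assumption): 0
- leavers at 75%: 0.20 × (−0.15) = −3 points

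**Step 3: effect of other procedures.** Bias among those seen = share with a procedure × (their response rate with it − their rate without it). At a 10% share:

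- 100% against 0%: +10 points
- 80% against 40%: 0.10 × 0.40 = +4 points
- no change in response: 0

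**Step 4: both together at 20% missing.** If 5 of the 101 seen responded only because of another procedure, 56/101 = 55.4% on observed cases and 56/126 = 44.4% with leavers also non-responders. If 10 did, 51/101 = 50.5% and 51/126 = 40.5%.

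**Step 5: what the planned tables already allow.** Table 3-20 shows N and n at each visit, and Table 3-5 shows missed and withdrawn subjects. A reader can therefore work out the missing-as-non-responder rate. The rate after recoding post-procedure ratings cannot be recovered: SAP 2.3.4 summarises concomitant procedures by group, and no planned table links them to response at a visit.

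**The case against.** The strongest reply is that the upward direction is not established. A reader might infer that both features necessarily inflate the late rates. The documents do not support that: the SAP carries the hot-deck assumption alongside BOCF, and Step 2 shows the sign can be zero or negative. This stands, so the point is conditional.

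Nor is the handling of other procedures written for Months 18 and 24. The SAP's phrase "irrespective of use of not allowed treatments, procedures, or medications" covers only the two primary-analysis alternatives. For the late visits the handling is inferred from Protocol 4.6 with SAP 2.4.1 and 2.4.2. The inference is sound, but it is an inference. The prohibited list also includes items such as neurotoxin and chemical peeling that need not raise an MMVS response, and exclusion criteria 18 and 20 screen out subjects likely to seek other procedures.

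It is also fair that no duration endpoint is defined, that the late results have no test or success rule, and that the OC label is open. Table 3-20 gives a Month 12 observed-case row for a like-for-like comparison with later visits.

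Finally, a reader might infer that early ratings would fall into the Month 24 row, because the two visits share a heading in Protocol 4.8.1.6, with the line "Laboratory tests (Only performed at early termination if termination occurs before 12 months visit". That line concerns laboratory tests. Month 24 has its own window of ±4 weeks from baseline, and Protocol 5.5 provides a separate early-termination eCRF. Such misassignment is speculation.

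What survives all this is that neither feature has any sensitivity analysis after Month 12, and the second cannot be reconstructed from the planned tables.

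**Conclusion.** The concern holds in conditional form. The Month 18 and 24 rates can overstate persistence if leavers respond less than stayers, as the SAP assumes for its primary BOCF analysis, or if prohibited volume-adding procedures turn non-responders into responders. If leaving is unrelated to effect and no such procedures occur, there is no bias.

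On the assumed figures, 60.4% falls to 48.4% for leavers alone, and to 44.4% or 40.5% with procedures added. The largest gap, 60.4 − 40.5 = 19.9 points, is tempting to read as the expected overstatement. It is not: it needs every leaver to be a non-responder and all ten procedure subjects to owe their response to the procedure, on rates the documents do not give. Intermediate assumptions give about +6 points for leavers and +4 for procedures. The Month 12 primary conclusion is unaffected. This is a modest but worthwhile correction to descriptive secondary endpoints.

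**What to change.** In SAP 2.4.2 and 2.4.4, state how ratings after a prohibited volume-adding midface procedure are handled at Months 18 and 24. Then:

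- Keep the observed-case rows in Tables 3-20, 3-22, 3-25 and 3-27. For Months 18 and 24, add a supplementary row with all Sculptra FAS subjects in the denominator. Count as non-responders those without a rating and those with a recorded filler, fat, thread or implant procedure in the midface before that visit. Label it a conservative bound.
- In Table 3-24, show 3D volume with and without post-procedure values, with the number affected. Exclusion alone would drop the subjects most likely to have faded and so reintroduce selection.
- Optionally, add one sentence assigning early-termination ratings to visits by actual date.

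The cost is SAP wording and a few table rows. Concomitant procedures are already recorded at every visit, so no new data are needed. The drawback is that the added rate is conservative by construction and fails a subject who merely missed one visit, so it belongs beside the observed-case figure and should not replace it.

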2.4.3 Primary effectiveness analysis

The percentage of responders (a responder will be defined as a subject with at least 1 point improvement from baseline MMVS on both sides of the face concurrently) will be calculated at 12 months after baseline both in Treatment Group (denoted as π_{12M} Sculptra) and Control Group (denoted as π_{12M} Control) based on the blinded evaluator's assessment.

The null hypothesis $H_0: \pi_{12M}$ Sculptra = π_{12M} Control will be tested against the alternative hypothesis $H_1: \pi_{12M}$ Sculptra $\neq \pi_{12M}$ Control by using a Fisher's exact test at a significance level of 5%. In addition, for each group and also for the difference between the two groups the two-sided 95% confidence intervals around the estimates of the percentage of responders will also be calculated. The treatment will be deemed a success if the p-value for the treatment difference on the primary endpoint is less than 0.05 (i.e. the proportion of responders is statistically significantly larger in the Treatment Group compared to the Control Group).

Subgroup analyses by site will be performed for the primary analysis. The difference in responder rates along with the 95% confidence intervals will be presented for each each site. No formal statistical testing will be carried out for the subgroup analysis.

In addition, to obtain an estimate of the true clinical treatment effect, the primary analysis will be re-run using the PP analysis set.

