2.7 Determination of Sample Size

There are no available clinical data for Sculptra studied under conditions similar to the current study. However, based on what is seen in clinical studies of injectable fillers in the facial areas, it is

 GALDERMA	<small>Title</small> 43CHSA1803 Statistical Analysis Plan - Sculptra China	<small>Doc id</small> MA-40407
---	--	--

2019-10-24 08:59

Effective date:

Effective

reasonable to assume a response rate of at least 60% in the Sculptra Treatment Group at Month 12. For the no treatment Control Group, response rate of 25.8% has been observed in an ongoing clinical trial in China. Based on this, it was assumed that the response rate will be maximum 30% in the no-treatment Control Group at Month 12.

With a sample size of 100 subjects treated with Sculptra and 50 subjects in the no-treatment control group, Fisher's Exact test will have approximately 90% power to detect difference between the anticipated percentage of responders at a 5% significance level (two-sided). To account for 20% drop-outs, approximately 126 will be randomized to the Sculptra group and approximately 63 to the control group.

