**Table 3-16: Subjects reporting concomitant medication, FAS**

	Sculptra N = XX				Control N = XX			
	No		Yes		No		Yes	
	n	%	n	%	n	%	n	%
Ongoing at study start								
Initiated during study								
Total								

 $\% = (n/N)*100$

Note: A single subject might have had concomitant medication ongoing at study start and initiated during study

Table 3-17: Subjects reporting concomitant medication and number of medications by reason, FAS

Reason for concomitant medication	Sculptra N = XX				Control N = XX			
	Subjects		Number of medications		Subjects		Number of medications	
	n	%	Total	Ongoing at study end	n	%	Total	Ongoing at study end
Related Adverse Event								
Unrelated Adverse Event								
Medical History								
Other								
Total								

 $\% = (n/N)*100$

Note: A single subject might have reported concomitant medication for several reasons

Table 3-18: Subjects reporting concomitant medication and number of medications by ATC code, FAS

ATC code	ATC text	Sculptra N = XX		Control N = XX		
		Subjects		Number of medications	Subjects	
		n	%		n	%
	Total					

$\% = (n/N) * 100$

Note: A single subject may have reported several types of concomitant medication

Concomitant procedures

In a similar way as for conmed

Efficacy

Table 3-19: MMVS responder rate at Month 12 by treatment (both sides of the face combined), Blinded Evaluator

Population	Visit	Treatment	Subjects		Responders		95% Confidence interval			p-value
			N	n	n	%				
FAS ¹⁾	Month 12	Sculptra								
		Control								
		Difference								
PP ²⁾	Month 12	Sculptra								
		Control								
		Difference								
FAS ³⁾	Month 12	Sculptra								
		Control								
		Difference								

1) Note: Missing values at Month 12 are imputed using the BOCF method.

2) No imputation is used for PP analysis. Only subjects with complete data are included.

3) Note: Missing values at Month 12 are imputed using the Hot deck imputation method.

Note: Responder is defined as a subject with an improvement of at least one grade on the MMVS from baseline

Note: Responder rate (%) = $(n/N) * 100$

Note: P-values for the difference in proportions are based on the Fisher's Exact test.

Note: 95% confidence intervals are two-sided and calculated using the exact interval. For the difference, asymptotic confidence limits are used.

 GALDERMA	Title 43CHSA1803 Statistical Analysis Plan - Sculptra China	Doc id MA-40407
--	---	---------------------------

2019-10-24 08:59

Effective date:

Effective

Version: 1.0

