Table 3-20: MMVS responder rate over time (both sides of the face combined), Blinded Evaluator, FAS, OC

Visit	Treatment	Subjects	Responders			95% Confidence interval			p-value
			N	n	%				
Month 6	Sculptra								
	Control								
	Difference								
Month 9	Sculptra								
	Control								
	Difference								
Month 12	Sculptra								
	Control								
	Difference								
Month 18	Sculptra								
Month 24	Sculptra								

Note: Responder is defined as a subject with an improvement of at least one grade on the MMVS from baseline.

Note: Responder rate (%) = $(n/N) * 100$

Note: P-values for the difference in proportions are based on the Fisher's Exact test.

Note: 95% confidence intervals are two-sided and calculated using the exact interval. For the difference, asymptotic confidence limits are used.

Note: The main study consists of visits up to 12 months

Figure 3-1: MMVS responder rate over time (both sides of the face combined), Blinded Evaluator, FAS, OC

Effective date: 2019-10-24 08:59

Effective

Version: 1.0

Table 3-21: MMVS over time, Blinded Evaluator, FAS, OC

Visit / Treatment			Side	MMVS								
				1 – Fairly full		2 – Mild loss		3 – Moderate loss		4 – Substantial loss		Total
Baseline	Sculptra	Left		n	%	n	%	n	%	n	%	N
		Right										
Month 6	Sculptra	Control	Left									
		Right										
	Control	Left										
		Right										
Month 9	Sculptra	Left										
		Right										
	Control	Left										
		Right										
Month 12	Sculptra	Left										
		Right										
	Control	Left										
		Right										
Month 18	Sculptra	Left										
		Right										
Month 24	Sculptra	Left										
		Right										

% = (n/N)*100

Note: The main study consists of visits up to 12 months

Table 3-22: MMVS responder rate over time (both sides of the face combined), Treating Investigator, FAS, OC

Same as for Blinded Evaluator

Figure 3-2: MMVS responder rate over time (both sides of the face combined), Blinded Evaluator, FAS, OC**Table 3-23: MMVS over time, Treating Investigator, FAS, OC**

Same as for Blinded Evaluator

	Title 43CHSA1803 Statistical Analysis Plan - Sculptra China	Doc id MA-40407
--	---	---------------------------

Effective date: 2019-10-24 08:59

Table 3-24: Volume change (mL) over time (both sides of the face combined) as measured by digital 3D photography, FAS

Visit / Treatment		N	Mean	SD	Median	Minimum	Maximum
Month 6	Sculptra						
	Control						
Month 9	Sculptra						
	Control						
Month 12	Sculptra						

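### The supportive hot-deck row of SAP Table 3-19 treats one random draw per missing Month 12 score as observed data, so its variance is understated and its result depends on the draw; the primary BOCF test is not affected

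*SAP*

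**What the plan says.** SAP 2.4.2 makes BOCF the primary handling of missing Month 12 data and offers the hot deck as an alternative, for the case where missingness is unrelated to treatment effect. The hot-deck rule is: "Each missing value in MMVS at Month 12 visit (recipient) will be imputed with a non-missing (observed) value from a subject randomly selected". Donor and recipient must share a class. Classes are formed by arm, baseline MMVS (2, 3 or 4) and age (under 55, or 55 and over), and other classes are allowed at discretion. Neither document gives a number of draws, a combining rule, a variance adjustment or a seed. Protocol 10.6 leaves the detail to the SAP.

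Table 3-19 gives the hot deck one FAS row. Its notes read "Missing values at Month 12 are imputed using the Hot deck imputation method", then "P-values for the difference in proportions are based on the Fisher's Exact test", and "95% confidence intervals are two-sided and calculated using the exact interval. For the difference, asymptotic confidence limits are used". The same notes serve the BOCF and per-protocol rows. The SAP does not use the term single imputation, but one donor, one row and an ordinary Fisher test leave no other natural reading.

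Two further passages bear on the point. SAP 2.4.3 defines success: "The treatment will be deemed a success if the p-value for the treatment difference on the primary endpoint is less than 0.05". Table 3-20, titled "MMVS responder rate over time (both sides of the face combined), Blinded Evaluator, FAS, OC", includes Month 12 and has a p-value column.

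**The concern.** A donated score repeats information already in the observed sample. Counting it as a new observation gives the row a sample size it does not have, and the random choice of donor adds noise that the test and interval ignore. The row's interval comes out narrower than the interval from the observed subjects alone. A sensitivity analysis meant to test robustness then overstates certainty, most of all when most data are missing.

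The rule also leaves three things open:
- MMVS is scored per side and response needs both sides, but it is not stated whether one donor supplies both sides or each side has its own donor.
- The class uses a single baseline value, whereas Protocol exclusion criterion 21 admits subjects whose sides differ by one point.
- Classes may be changed without a rule.

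At stake is how this supportive row reads in the report.

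**Working it through.** **The plan's own figure.** For 100 versus 50 subjects at 60% versus 30%, two-sided 5% Fisher, the Walters arcsine approximation gives 91.8% power and exact enumeration 92.7%; the SAP says about 90%. Drop-out: 100/0.8 = 125 and 50/0.8 = 62.5, rounded up to 63, against "To account for 20% drop-outs, approximately 126 will be randomized to the Sculptra group and approximately 63 to the control group". These agree closely enough.

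**Inputs.** 126/63 randomized, two-sided 5% Fisher, asymptotic interval for the difference (taken as Wald), all from the SAP. Null response is 30% in both arms, following SAP 2.7, where "it was assumed that the response rate will be maximum 30% in the no-treatment Control Group at Month 12". Assumptions: 5%, 10% or 20% missing, completely at random and equal in both arms; donors drawn with replacement within arm; both sides from one donor.

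**Variance by hand.** With n randomized, o observed and m = n − o missing in an arm, the completed rate has variance p(1−p) × [1/o + (m/n²)(1 − 1/o)]. Table 3-19 in effect uses p(1−p)/n. The ratio is

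n/o + (m/n)(1 − 1/o).

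At 20% missing:
- Sculptra (o = 101, m = 25): 126/101 + (25/126)(100/101) = 1.248 + 0.196 = 1.444.
- Control (o = 50, m = 13): 63/50 + (13/63)(49/50) = 1.260 + 0.202 = 1.462.
- Difference, weighting by 1/126 and 1/63: (1.444 + 2 × 1.462)/3 = 1.456, so the SD is √1.456 = 1.21 times what the analysis assumes.

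The same steps give 1.05 at 5% and 1.10 at 10%. For a normal test, 1.96/1.207 = 1.62, a two-sided error of about 10.4% at 20% missing. Fisher's test is conservative (4.1% with complete data) and absorbs part of this.

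**Simulation** (400,000 trials per scenario):

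| Missing | Fisher type I error | Sculptra direction (nominal 2.5%) | Coverage of difference CI |
|---|---|---|---|
| 0% | 4.1% | 2.1% | 94.4% |
| 5% | 5.1% | 2.7% | 93.2% |
| 10% | 6.3% | 3.2% | 91.8% |
| 20% | 9.0% | 4.5% | 88.7% |

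Drawing within six baseline-by-age classes per arm (assumed class mixes) gives 8.8–9.1% at 20% missing, so ignoring the classes does not create the effect. Drawing without replacement gives about 8.4–8.5%. Separate donors per side (assumed side rate 35%, both sides 30%) give 4.8%, 5.6% and 7.2%. Fisher on the observed cases stays near 4%.

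**Precision.** At 20% missing the average half-width is 13.7 points for the hot-deck row and 15.4 for observed cases. By hand at exactly 30%: 1.96 × √[0.21 × (1/126 + 1/63)] = 13.9 and 1.96 × √[0.21 × (1/101 + 1/50)] = 15.5 points.

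**Dependence on the draw.** Suppose 52/101 versus 17/50 are observed. Fisher on observed cases gives p = 0.056 and BOCF (52/126 versus 17/63) gives p = 0.057. Over 100,000 redraws, 73% give p < 0.05, and p runs from 0.003 to 0.16 (5th to 95th percentile). At the planned effect (61/101 versus 15/50) more than 99.9% of redraws are significant.

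**The case against.** The strongest reply is that nothing decisive rests on this row. BOCF is primary, success is tied to the primary p-value, and the observed-case Month 12 row in Table 3-20 is correctly sized under the same missing-data assumption. That stands, and it limits the harm to how one supportive row is read.

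The upper figures also need qualifying. No document gives an expected Month 12 missing rate, and 20% is the sample-size allowance. At 5% missing the error is about nominal. A donor per side is arguably the more literal reading and lowers the 20% figure to about 7%. These limits stand too.

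A reader might infer that the row's p-value is always too small. It is not: a single draw can move p either way, and in the example above 27% of redraws are not significant. The defect is an understated variance plus dependence on the draw.

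A reader might also infer a raised risk of a false success claim. The documents do not support that. Success follows the BOCF test, and under the null at 20% missing BOCF and the hot deck both favour Sculptra significantly in only about 1.5% of trials.

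What the reply does not remove is that the p-value and intervals of this row, as specified, do not have their stated error rate or coverage once about 10% of the data are missing.

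**Conclusion.** The point holds for the hot-deck row of Table 3-19 only. With one whole-subject donor, 30% response in both arms and data missing completely at random, two-sided type I error is about 5%, 6% and 9%, and coverage about 93%, 92% and 89%, at 5%, 10% and 20% missing. With separate side donors, type I error is about 5 to 7%. The variance formula and the simulation agree on the cause. The success decision is unaffected, and at 60% versus 30% the row is significant in about 95 to 97% of trials, so the draw matters only near the boundary. This should be corrected because the remedy is small; it is not a threat to the trial's conclusion.

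**What to change.** Amend SAP 2.4.2 and Table 3-19 in one of two ways.

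**(a) Multiple hot-deck imputation.** Use an approximate Bayesian bootstrap with at least 50 draws and a fixed seed, and combine the risk difference by Rubin's rules. Take both side scores from one donor, or impute responder status directly. State which baseline value defines the class when the sides differ. Keep classes no finer than the present six per arm, and fix in advance the order in which classes without donors are collapsed.

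Cost: SAP wording and some programming, and a Wald-type test in this row instead of Fisher (the planned interval for the difference is already asymptotic). With draws within arm, type I error becomes 5.3–5.5% (complete-data Wald: 5.6%) and coverage 94.5–94.7%. With small classes at 20% missing, type I error is about 6%; a short run of 2,000 trials with six classes and 10 draws gave 6.7%. The half-width at 20% missing grows from about 13.7 to 15.5 points. Power of the row at 60% versus 30% and 20% missing stays near 95%. The gain at 20% missing is 9.0 − 5.5 = 3.5 points of type I error with draws within arm and nearer 3 with small classes. At 10% it is at most about 1 point, and at 5% there is none.

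**(b) No new programming.** Remove the p-value and confidence intervals from the hot-deck row, keep its point estimates, and name the observed-case Month 12 row of Table 3-20 as the inferential check under the same missing-data assumption. SAP 2.4.4 lists blinded-evaluator tests only at Months 6 and 9, so the text should say that this Month 12 row carries the test.

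The primary analysis does not change under either option.
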